Subjects are presented with study drug (OXE-103) treatment. If they decline, they will be offered participation in non-treatment control Arm. If subjects choose treatment and fail screening, they may be offered non-treatment control Arm option.

PART A ARM 1 = OXE-103 treatment

PART A ARM 2 = Non-treatment concurrent control

[figure not shown]

PART B: ACUTE DAY 1

Subjects choosing to participate in study are randomized to receive study drug (OXE-103) or placebo.

PART B ARM 1 = OXE-103

PART B ARM 2 = Placebo

Regulatory:

Oxeia's license through Daiichi Sankyo includes cross-reference to an open IND at the FDA. In November 2017 Oxeia submitted a pre-IND briefing package for a proposed Phase 2 study. The FDA response supported moving into Phase 2. This study will be conducted under an investigator sponsored IND cross referencing the existing open FDA IND.

Manufacturing, Partnerships, Current GMP Drug Supply:

The company maintains access to clinical grade drug supply manufactured by Daiichi Sankyo, Ltd. for subcutaneous injection. Multiple lots have been produced and are available for clinical study use. The drug product is manufactured in compliance with good manufacturing practice. It is supplied in a 5 mL clear, borosilicate glass vial with a butyl-rubber closure (fluoro-resin film laminated), as a sterile lyophilized white powder or cake equivalent to 14 mg of OXE-103 as the active ingredient and sucrose (inactive ingredient). Matching placebo and diluent product is also available.

OXE-103 drug product, placebo, and diluent should be stored refrigerated between 2°C to 8°C (35.6°F to 46.4°F). Reconstituted OXE-103 for SC administration 14 mg (in 5 mL multi-use vials) is stable for up to 14 days at 10°C or for up to 3 days when stored at 25°C/1000 Lux. The reconstituted drug product (and placebo) should be stored refrigerated at 2°C to 8°C (35.6°F to 46.4°F).

Upon request from the study team, Oxeia Biopharmaceuticals will coordinate shipment of all necessary study drug product, placebo, and diluent to the study team. Shipments will include all appropriate certificates of quality, as may be necessary for any FDA-related audits and submissions.

Proposed Clinical Trial

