We propose a pilot study to treat 1) Sub-acute concussion with OXE-103 in Part A and 2) Acute concussion management with OXE-103 within 24 hours of presentation to the Trauma Unit in Part B. For Part A, we will recruit subjects from the University of Kansas Health System Center for Concussion Management (CCM) clinics which include Neurology, Sports Medicine, and Neurosurgery/PM&R. For Part B, we will recruit subjects from the University of Kansas Health System Trauma Unit. In Part A we will compare an open-label treatment arm (OXE-103) to a non-treatment concurrent control arm. Part B will be randomized double blind 1:1 to treatment with OXE-103 and placebo. We will compare these using self-report symptom scoring, quality of life questionnaires, computerized cognitive testing assessing executive function, memory and processing speed, and accelerometer-based balance scoring. The exploratory nature of this study is not powered to yield statistically significant outcomes, but will allow detection of trends within subjects and between groups, will support comparison with standard tests of neurocognitive functions, and will provide sample size estimates for future studies of people with persistent concussion related symptoms.

This study is highly relevant clinically and uniquely suited to being conducted at the CCM. It will be the first to test ghrelin as therapy for sub-acute concussion.

Specific Aims:

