Subjects will be both men and women, ages 18-60 years old, with a concussion resulting from a direct or indirect blow, rotation, or whiplash injury to the head or body. For the purposes of this study, we will define diagnosis of concussion/mTBI as those who have met the criteria set forth in this classification schema [23]:

Severity of Traumatic Brain Injury			
	GCS	PTA	LOC
Mild	13-15	<1 day	0-30 mins
Moderate	9-12	>1 to < 7 days	>30 mins to < 24 hrs
Severe	< 9	> 7 days	> 24 hrs

*GCS=Glasgow Coma Scale; PTA=Post-Traumatic Amnesia; LOC=Loss of Consciousness

However, as noted by the American Congress of Rehabilitation Medicine's statement on the definition of mTBI, "Due to the lack of medical emergency, or the realities of certain medical systems, some patients may not have the above factors medically documented in the acute stage. In such cases, it is appropriate to consider symptomatology that, when linked to a traumatic head injury, can suggest the existence of a mild traumatic brain injury [24]. When available, the study team will use medical records to confirm a patient's injury as an mTBI according to the schema above, however, if no records exist or are obtainable, clinical history and symptomatology will be used to confirm the diagnosis.

In Part A, subjects must be consented \leq 28 days post injury. In Part B, subjects must be consented, randomized, and start treatment within 24 hours of presentation to the Trauma Unit.

Subjects in both Part A and B will have a symptom severity score of ≥ 20 at the time of randomization in order to reduce the expected degree (number and severity) of spontaneous symptom resolution prior to study completion.

Subjects with pre-existing neurologic conditions other than mTBI (including cognitive dysfunction) will be excluded.

Subjects with concurrent long bone fractures or orbital fractures will be excluded.

Subjects receiving, or planning to receive, a continuous ketamine infusion while enrolled in study will be excluded.

Subjects with these known endocrinological abnormalities at baseline will be excluded from study: diabetes mellitus, excess or deficiency of growth hormone, cortisol, or prolactin. Exclusion from study for any other endocrinological abnormalities or diagnoses existing at baseline are ultimately up to the discretion of the study physician.

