Subjects will be provided with instructions for SC self-administration of OXE-103 and placebo. Subjects will be trained to inject themselves and need to demonstrate competency by self-administering the first dose of the study drug at the study site. Alternatively, if a subject is accompanied by a reliable and willing household member, that individual will be trained to administer study drug to the subject and will be required to demonstrate competency at the study site. If neither self-administration nor administration by a household member is feasible the subject will be deemed ineligible to participate. Subjects will also be instructed on storage of the drug/placebo according to the parameters. A study team member will document the storage location for each subject enrolled. Subjects will be asked to inject the first daily dose in the morning, after eating. The second dose will occur in the evening, again after eating. The study team may provide injection diaries to subjects in order to document dosing.

Recruitment:

Subject recruitment for Part A will take place among patients seen in [name] for Concussion Management (CCM) clinic located at The University of Kansas Health System (TUKHS), Landon Center on Aging, Department of Neurology. Subject recruitment for Part B will take place among patients seen by the TUKHS Trauma team. Patients meeting the study's

inclusion/exclusion criteria will be invited to participate in the study. If they are interested, a study team member will meet with the patient to discuss the study in more detail. Informed consent will be sought; when obtained, subjects will be screened for study risks and other exclusion criteria. Subjects enrolled in Part B of the study by the Trauma team will be followed after discharge from the hospital in [name] clinic; the remainder of their study visits will be completed with [name] in his ambulatory clinic. Part A Arm 1 (non-treatment control) study visits may be conducted via telemedicine at the discretion of the Principal Investigator, [name], with the exception of Study Days 1 and 15 when correlative labs will need to be drawn, and Day 44 when study iPads will need to be returned to the study team.

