Subjects will complete the PCSS at the following timepoints[17]: upon signing consent (score must ≥ 20) (Day 1), as well as days 4, 8, 11, 15, 21 and 44. Subjects will be instructed to record their symptoms at the same time of day for each assessment timepoint. There can be a two-hour window either way. (e.g. 12PM +/- 2 hrs.). The PCSS is a self-reported assessment of 22 symptoms using a Likert-type scale ranging from 0-6, with 0 indicating no difficulty with the outlined symptom and ratings of 1-6 representing mild-to-severe difficulty with the symptom. The reliability and validity of the PCSS are well documented [18-20]. We will also ask subjects to rank their 4 most burdensome symptoms (4MBS) at Day 1 and we will analyze these separately. As stated in the Specific Aims the purpose of this study is to collect data that would further refine clinical endpoints that could be used for larger Phase 2 studies and possibly lead to the establishment of pivotal endpoints for Phase 3 registration trials. The 22 symptom PCSS assessment is designed to cover the full spectrum of concussion related symptoms across cognitive, emotional and somatic domains. In that regard the PCSS is particularly useful for diagnosis and monitoring recovery of patients post injury. However, due to the number of symptoms across cognitive, emotive and somatic domains, resolution of several mild symptoms may result in a change in the overall symptom score with relatively minor clinical impact on the patient's well-being. Pre-IND feedback already obtained from the FDA has noted that an effective therapy for concussion must impact the way a patient feels or functions. By including a specific analysis of the patient perceived 4MBS we are likely to be able to correlate symptom scores with improvement in the quality of life tools also being used in the study. The completion of the PCSS will take an estimated 5 minutes.

Quality of Life (AIM 2): A secondary goal is to examine change in quality of life with treatment of acute and sub-acute concussion. We hypothesize that OXE-103 will reduce symptoms when comparing days 1 and 15 and therefore improve quality of life as assessed by 1) Quality of Life after Brain Injury scale (QOLIBRI) and 2) a PGAS.

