6.1 General Methods

This pilot study will describe changes observed in the two treatment groups, placebo versus OXE-103, separately for each part. Since the study is exploratory, analyses will focus on descriptive comparative statistics and not on a pre-specified statistically significant primary endpoint. Data will be used to enable power calculations and the definition of suitable clinical endpoints for further clinical development. Data from baseline and on Study Days 4, 8, 11, 15, 21, and 44 will be analyzed. Note that day definitions in this study will follow the Clinical Data Interchange Standards Consortium in that there is no Day 0;

assessments performed prior to randomization will be done on Days -7 and -3 (Part A only) and randomization is considered Day 1.

For all evaluations of changes from baseline, baseline is defined as the last reported value before the first dose of study drug. In most instances, this will be the value recorded on Day 1.

For the evaluation of safety, a treatment-emergent finding is any result that is newly reported after the first dose of study drug. This may include an existing condition which worsens in severity after the start of treatment.

Continuous variables such as total score or change from baseline will be summarized by the number of observations, mean, standard deviation, median, minimum and maximum value. Graphs of changes from baseline over time will present the means and 95% confidence intervals.

Binary or categorical variables will be summarized by the number of observations in each category along with the percent of observations.

To aid in interpretation of the importance of relationships, correlation coefficients (Pearson and Spearman) will be reported with p-values.

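### Open-label Part A: the arm choice appears to come before the self-rated Day 1 baseline, so over-reporting by subjects who have chosen drug would count as improvement

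*Protocol*

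**What the plan says.** **Design.** Protocol, Proposed Clinical Trial: "In Part A we will compare an open-label treatment arm (OXE-103) to a non-treatment concurrent control arm". Arms are not randomized in Part A.

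**Arm choice.** Protocol, Part A: Post-acute Day 1: "Subjects are presented with study drug (OXE-103) treatment. If they decline, they will be offered participation in non-treatment control Arm". The next sentence reads: "If subjects choose treatment and fail screening, they may be offered non-treatment control Arm option".

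**Consent and screening.** Protocol, Recruitment: "Informed consent will be sought; when obtained, subjects will be screened for study risks and other exclusion criteria".

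**PCSS timing and cut-off.** Protocol, Outcomes & Study Tools (AIM 1): the PCSS is self-reported and is completed "upon signing consent (score must ≥ 20) (Day 1), as well as days 4, 8, 11, 15, 21 and 44". Inclusion/Exclusion states the cut-off for everyone: "Subjects in both Part A and B will have a symptom severity score of ≥ 20 at the time of randomization".

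**Baseline.** SAP 6.1: "baseline is defined as the last reported value before the first dose of study drug", which the SAP expects to be the Day 1 value in most instances.

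**Ordering rule.** The footnote to the Part A Arm 1 Schedule of Events requires Day 1 and Day 8 questionnaires to be finished before drug is dispensed. It does not mention the arm choice.

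**Use of the baseline.** The primary aim is the change from Day 1 to Day 15. SAP 5.1 defines three responder outcomes (severity, number of symptoms, 4MBS severity), each as an improvement of at least 20% over baseline. SAP 6.13 rules out covariate adjustment.

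**The concern.** The Day 1 PCSS both decides entry and serves as the starting point for every primary outcome. If it is rated after the arm choice, a subject who expects the drug rates symptoms with that in mind, and a subject who has declined does not. Any upward shift in Arm 1 alone lowers the real recovery needed to be counted a responder and enlarges the mean change. The 4MBS severity, QOLIBRI and PGAS baselines are self-rated on the same day and share the exposure.

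The current schedule starts at Day 1, so no earlier study score exists as a check. Part B does not have this asymmetry, because its double blind prevents either arm from rating with knowledge of the allocation.

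Part A is descriptive, but its results are meant to show between-group trends, support power calculations and help define endpoints for later studies. An artefact in the Arm 1 baseline would carry into each of these uses.

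**Working it through.** **1. Order of events on Day 1.** No single sentence gives it; three passages have to be combined.
- The Part A flow lets a subject choose treatment and then fail screening, so the choice precedes screening.
- Recruitment puts screening after consent.
- AIM 1 puts the PCSS at consent with a required score of at least 20, so it belongs to that screening.

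The implied order is drug offered, arm chosen, PCSS rated. The footnote requirement (before dispensing) is compatible with this order and does not prevent it.

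**2. Effect on the 20% rule.** Let T be the true Day 1 score, k the over-report and r the true proportional fall, with Day 15 rated accurately. A responder needs T(1 − r) ≤ 0.8(T + k), that is r ≥ 1 − 0.8(T + k)/T.
- T = 30, k = 3: 1 − 0.8 × 33/30 = 12%.
- T = 20, k = 3: 1 − 0.8 × 23/20 = 8%.
- No real change at all: the over-report needed is 1/0.8 − 1 = 25%, for example a true 16 reported as 20.

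**3. General over-reporting in Arm 1.** The documents give no PCSS mean or SD, so all inputs here are assumptions. There is no drug effect and no inflation in Arm 2.

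Model 1: T uniform on 20 to 60; r normal with mean 30% and SD 35%; the same k for every Arm 1 subject; 400,000 simulated subjects.

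| k (points) | Severity responders | Excess over k = 0 |
|---|---|---|
| 0 | 61.4% | – |
| 2 | 66.0% | 4.6 |
| 3 | 68.3% | 6.9 |
| 5 | 72.6% | 11.2 |

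Direct integration of the formula in step 2 gives 61.2, 65.9, 68.2 and 72.5%, in agreement.

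Model 2: T about normal with mean 35 and SD 18; reporting error SD 5; entry at a reported score of at least 20; recovery SD 30 percentage points; mean recovery 0, 20 or 40%.

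| Arm 1 inflation | Excess mean change (points) | Excess responders (percentage points) |
|---|---|---|
| 5% | 1.8 to 2.0 | 3.4 to 4.4 |
| 10% | 3.7 to 4.0 | 6.7 to 8.6 |
| 25% | 9.2 to 9.7 | 14.4 to 21.3 |

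**4. Lifting scores only to pass the cut-off.** In model 2, raising reported scores of 15–19 to 20 affects about 8% of Arm 1. It adds 1.1, 0.7 and 0.2 percentage points to the responder rate at mean recovery of 0, 20 and 40%. The mean change moves by +0.1, −0.3 and −0.6 points, so on average it is not overstated. In model 1, extended below 20, the responder rate goes from 61.3% to 62.6% (+1.3); lifting only 17–19 gives 61.8%.

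**5. Scale.** With 20 completers per arm, 5 to 11 percentage points is 1 to 2 subjects. The standard error of a difference at 61% is √(2 × 0.61 × 0.39/20) = 0.154, about 15 percentage points.

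**The case against.** **The order is not stated.** A reader might take the protocol to set choice-then-PCSS outright. It does not. The order is inferred, Recruitment also speaks of inviting patients who already meet the criteria, and the Day 1 flowsheet, which is not shown, may settle it. This stands as a limit on certainty. It does not remove the point, because no visible text puts the baseline first.

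**The cut-off is not a gate to the drug alone.** A reader might infer that the score of 20 drives the inflation. The cut-off is written for both arms, nothing visible says subjects are told of it, and step 4 shows that its own contribution is small. This objection stands in full. The exposure is general over-reporting by subjects who expect drug.

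**The contrast is diluted.** Subjects who sought drug and failed screening may enter Arm 2, so some Arm 2 baselines carry the same incentive. This stands. Read literally, the entry criterion would bar a failure on the PCSS itself from Arm 2, while the Part A flow makes no such exception; the two passages should be reconciled.

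**The illustration covers one outcome.** Rating existing symptoms higher does not change the number of symptoms, so the symptom-count responder is less exposed. So is the protocol's definition in Statistical Analysis, which requires a 20% reduction in both number and severity. This stands.

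**Materiality.** Part A is an unpowered pilot, the illustrated excess is below one standard error, and self-selection and unblinded Day 15 rating would remain in any case. This argues for modest priority. It does not argue for keeping a bias that reordering can reduce cheaply, since a systematic shift does not average out as sampling error does.

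**Conclusion.** The point holds as a risk in the design. The visible text implies that Part A baselines are rated after the arm choice, and nothing visible prevents it. Because the comparison is open-label and unadjusted, over-reporting confined to Arm 1 would be read as benefit. Adjusting for baseline would reduce but not remove the bias, because the baseline itself would be distorted.

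The size is unknown. The 5 to 11 percentage points depend entirely on assuming that every Arm 1 subject over-reports by 2 to 5 points, and on assumed score and recovery distributions. A reader might take that range as an estimate of bias in this trial; the documents contain nothing that shows inflation occurs or how large it is. Lifting scores to reach 20 contributes only about 0.2 to 1.3 points under the two models. This is a cheap improvement to Part A and does not call Part B into question.

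**What to change.** **Protocol, Part A Day 1.**
- Obtain consent to the baseline assessments common to both arms.
- Complete and lock the PCSS, 4MBS ranking, QOLIBRI, PGAS and BrainCheck.
- Only then present the drug option and record the arm. Moving only the recording of the choice would not be enough, because a subject already offered the drug would still rate with it in mind.
- Apply the existing PCSS entry criterion to the locked score in both arms, and replace its reference to randomization, which Part A no longer has.
- If the clinic or the flowsheet already follows this order, state it in the text.

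**SAP.**
- Define the locked assessment as the Part A baseline. The present definition depends on a first dose, which Arm 2 never receives, and SAP 2 still describes Part A as randomized and double-blind with a 7-day screening period.
- Report baseline scores by arm and, within Arm 2, by route of entry (declined drug, or chose drug and failed screening).
- Describe Part A between-arm differences as non-randomized.

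**Cost.** A two-step consent, and some subjects who complete the assessments and then join neither arm. All the assessments are already scheduled for Day 1 in both arms, so no visit or test is added. Self-selection into arms and unblinded rating at Day 15 are not cured.

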- 1. Describe the change in symptom burden in sub-acute (Part A) and acute (Part B) concussion for the two groups.** This aim defines our primary objective. In Part A we will enroll a maximum of 30 subjects in the open-label treatment Arm (OXE-103) but will stop recruiting when that arm has 20 participants who have completed study requirements. All Part A participants must be diagnosed with a concussion and experience persistent concussion symptoms \leq 28 days post injury. The Part A non-treatment concurrent control Arm will enroll a minimum 20 participants who complete the study requirements, but may continue to recruit more than 20 participants while the Part A open-label treatment Arm is still recruiting. In Part B we will enroll a maximum of 50 subjects but will stop recruiting after each arm (OXE-103 Arm and placebo Arm) has 20 participants who have completed the study requirements. In Part A subjects will receive OXE-103 open-label and in Part B we will randomize 1:1 to placebo versus OXE-103. The Post-Concussion Symptom Score questionnaire (PCSS) will be used as an overall measure of symptom burden. The number of symptoms and severity at each time point are also measures of interest. In addition, subjects will be asked to identify and rank the 4 most bothersome symptoms. We hypothesize that changes in these most bothersome symptoms may have a higher correlation to improvement in quality of life. A visual comparison of change in the two groups will be made. We will consider a change of 20% to be clinically meaningful. Our primary aim will describe the change in symptoms between day 1 and day 15.
- 2. Describe the change in quality of life between the two groups.** This aim defines one of our secondary objectives. To assess this, we will administer the Quality of Life after Brain Injury scale (QOLIBRI) and a Patient Global Assessment of Status (PGAS). A change of 20% will be considered clinically meaningful. Our primary objective with this aim will assess the change between days 1 and 15.
- 3. Describe the correlation between the change in symptom burden and quality of life.** This is an exploratory aim. We hypothesize that improvement in symptom burden will correlate with improvement in quality of life measures. This may be more evident in the correlation between the change in the 4 most bother symptoms and quality of life measures. This aim will describe this correlation between days 1 and 15.

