In Part B the design will be randomized, double-blinded, and placebo-controlled with Arm 1 receiving OXE-103 and Arm 2 receiving placebo. The enrollment target will be 20 subjects receiving OXE-103 and 20 subjects receiving placebo. Up to 50 subjects may be enrolled in Arms 1 and 2 combined to allow for replacement of subjects who may not complete the study requirements.

In Part A Arm 1 and Part B both Arms 1 & 2, the maximum enrollment will be 80 subjects. For the Part A Arm 2 (non-treatment concurrent control) the minimum target enrollment will be 20 subjects, but there will be no maximum number.

We will randomize using the REDCap database. The database will be set up to share randomization allocation only with the statistician and Investigational Pharmacy. All subjects will be consented and either begin treatment within 24 hours of presentation to the Trauma Unit (for Part B) or ≤ 28 days post-injury (for Part A). For Part A, starting on Day 1, the treatment cohort (Arm 1) will receive OXE-103 40ug/kg twice daily by self-injection and the non-treatment control group (Arm 2) will begin their monitoring. For Part B, on Day 1 (within 24 hours of being admitted into the Trauma Unit) the treatment Arm will receive OXE-103 40ug/kg SC twice daily by self-injection and the placebo Arm will receive a placebo injection SC twice daily. OXE-103 and placebo will be maintained and dispensed by Investigational Pharmacy. Subjects will receive an 8-day supply of syringes pre-loaded with OXE-103 or placebo. Each cohort receiving OXE-103 or placebo will receive the 2nd set of syringes with OXE-103 or placebo at the Day 8 visit. Appropriate therapy that would be considered standard of care by the Principal Investigator or Co-Investigator will be administered or prescribed at any time during subjects' study participation.

Subject training

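### Part A's untreated control arm may take subjects who failed screening for OXE-103, with no stated limit on the reason, which conflicts with the protocol's single exclusion list

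*Protocol*

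**What the plan says.** The protocol's Proposed Clinical Trial section sets the contrast: "In Part A we will compare an open-label treatment arm (OXE-103) to a non-treatment concurrent control arm". Randomization applies to Part B only.

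The text under Part A: Post-Acute Day 1 gives Arm 2 two sources. The first is subjects who turn the drug down: "If they decline, they will be offered participation in non-treatment control Arm". The second is subjects who wanted it but did not qualify: "If subjects choose treatment and fail screening, they may be offered non-treatment control Arm option". No failed criterion is named as permitting or barring that step.

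The Inclusion/Exclusion section has one list and does not divide it by arm. One entry reads "Subjects with pre-existing neurologic conditions other than mTBI (including cognitive dysfunction) will be excluded". Others cover abnormal imaging, named endocrine disorders, laboratory limits, contraception and the ability to inject. The Arm 2 schedule of events keeps an inclusion/exclusion check on Day 1.

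Some criteria are restated more widely. Specific Aim 1 says "All Part A participants must be diagnosed with a concussion and experience persistent concussion symptoms", within 28 days of injury. On the symptom score, Inclusion/Exclusion says that subjects in both Parts "will have a symptom severity score of ≥ 20 at the time of randomization in order to reduce the expected degree" of spontaneous resolution. Outcomes & Study Tools (AIM 1) has the PCSS completed "upon signing consent (score must ≥ 20) (Day 1").

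Each Part A arm targets 20 completers. For Arm 2, General study design says "the minimum target enrollment will be 20 subjects, but there will be no maximum number".

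**The concern.** Specific Aim 1, the primary objective, describes symptom change from Day 1 to Day 15 in the two groups. A subject who fails screening can never be in Arm 1 but may be in Arm 2. If the failed criterion bears on recovery, as a neurologic condition or abnormal imaging plausibly could, the arms then differ in prognosis as well as in treatment.

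The protocol wants the pilot to show between-group trends and to supply sample-size estimates for later studies. A difference in who was eligible would pass into both, and enrolling more controls by the same routes would not reduce it.

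**Working it through.** The documents give no responder rate, standard deviation, effect size or power for Part A, so there is no figure of the plan's own to reproduce. The check is mainly a comparison of texts.

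**Step 1: which rule governs entry to Arm 2?**

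- If the single exclusion list binds Arm 2 in full, anyone who fails it is out of the study, and the screen-failure route admits nobody.
- If the screen-failure route operates, at least one criterion is waived for controls only, and the visible text does not say which.

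Both cannot hold as written.

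**Step 2: which criteria does other text secure for Arm 2?**

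| Criterion | Secured for Arm 2 beyond the general list? |
|---|---|
| Concussion with persistent symptoms, ≤28 days | Yes: Specific Aim 1 covers all Part A participants |
| PCSS ≥20 | Yes: stated for both Parts, and required at consent on Day 1 |
| Pre-existing neurologic condition | No |
| Abnormal imaging | No |
| Ability to inject, contraception, laboratory limits | No, but these can be read as concerning only receipt of drug |

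The exposure therefore lies mainly in the third and fourth rows. The PCSS row has a smaller defect: Inclusion/Exclusion ties the threshold to randomization, which Part A no longer has, while the Outcomes section ties it to consent.

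**Step 3: would the SAP reveal or remove the difference?**

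- Section 6.3 summarizes reasons for screen failure but does not link them to later membership of Arm 2.
- Section 6.4 counts entrance violations among randomized subjects, and Part A has none.
- Section 6.5 tabulates medical history by group, but Section 6.2 assigns that table to the randomized set.
- The per-protocol set in Section 6.2 removes major deviations, but it also requires at least 10 doses, so no Arm 2 subject can belong to it.
- Sections 6.12 and 6.13 plan no subgroups and no covariate adjustment.

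Nothing planned separates screen-failed controls from the rest.

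**Step 4: illustration of size, on assumed inputs.** Suppose the drug has no effect. Let *p* be the responder rate in eligible subjects, *p − d* the rate in screen failures, and *f* = *k*/20 the share of Arm 2 who are screen failures. The apparent difference is

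*p* − [(1 − *f*)*p* + *f*(*p* − *d*)] = *f* × *d*.

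- *k* = 2, *d* = 10 points: 2/20 × 10 = 1 point
- *k* = 2, *d* = 20 points: 2/20 × 20 = 2 points
- *k* = 5, *d* = 20 points: 5/20 × 20 = 5 points
- *k* = 8, *d* = 30 points: 8/20 × 30 = 12 points

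The values of *k* and *d* are assumptions, and *d* could be negative, which reverses the direction.

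For scale, the 95% half-width with 20 per arm and both rates at 60% (also assumed) is 1.96 × √(0.6 × 0.4/20 + 0.6 × 0.4/20) = 1.96 × √0.024 = 0.304, or 30 points. Over eligible rates of 50% to 70%, gaps of 10 to 30 points and any *f* from 0 to 1, it is about 28 to 31 points.

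**The case against.** The strongest reply is that the passages can be read together. Someone unsuitable for the drug may be offered Arm 2 at discretion, subject to Arm 2's own Day 1 check and to the study physician's general discretion over participation. On that view the text is incomplete but does not admit people with neurologic disease. The Day 1 flowsheet, which is not visible here, may also state conditions. This is a fair reading and may be what was intended. It stands as a reason not to claim that such subjects will be enrolled. It does not remove the problem, because the visible text never says which failures qualify.

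A second reply is that Part A is openly exploratory and unpowered, relies on a visual comparison, and has sampling error larger than any bias illustrated above. That is correct and limits the consequence. It does not excuse a systematic difference that can be prevented cheaply in data meant to guide later trials.

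Three stronger readings are tempting, and the documents do not support them:

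- **That Arm 2 is filled with screen failures.** Decliners are named first and are always to be offered the arm. Screen failures only may be offered it, and no number or share is given.
- **That a control could enter with a PCSS below 20,** so that a 20% improvement would mean a smaller change in one arm. The threshold is stated for both Parts and at consent, and no passage waives it for Arm 2.
- **That the absence of safety laboratory tests in Arm 2 is itself a flaw.** The protocol states this as a deliberate choice, and laboratory limits can reasonably be treated as conditions for receiving the drug.

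**Conclusion.** The concern holds in a limited form. The protocol contradicts itself on who may enter the Part A control arm. Read literally, its Day 1 text lets subjects with, for example, a pre-existing neurologic condition or abnormal imaging enter that arm only. The SAP would neither show nor adjust for the result.

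The size and direction of the bias cannot be derived from the documents. The 1 to 12 point range rests wholly on assumed counts and gaps, and it lies inside the sampling error of 20 per arm.

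A reader might infer that closing this route would make the Part A contrast a clean estimate of drug effect. It would not. Arm 1 chose the drug, the main source of Arm 2 declined it, and the outcome is self-reported without blinding. With no screen failures at all, the eligibility component would be zero (*f* = 0), but self-selection would remain.

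**What to change.** Reconcile the Day 1 arm-assignment text with Inclusion/Exclusion:

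1. State that criteria bearing on diagnosis and symptom course apply to both Part A arms: the mTBI definition, ≤28 days from injury, PCSS ≥20 on Day 1, and the imaging and neurologic exclusions.
2. State that a screen failure may enter Arm 2 only if the failed criterion concerns solely receiving study drug, for example ability to inject, contraception or pregnancy, or laboratory limits. The sponsor should assign each remaining criterion, such as the endocrine and fracture exclusions, to one group or the other.
3. For Part A, replace the reference to randomization in the PCSS criterion with Day 1 at consent, to match the Outcomes section.
4. Record for every Arm 2 subject whether they declined the drug or which criterion they failed.
5. In the SAP, report the Part A comparison with and without screen-failed controls. This first needs an efficacy set that an undosed, non-randomized subject can belong to.
6. State in the protocol and SAP that the Part A contrast is non-causal, because subjects choose their own arm.

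The cost is protocol and SAP wording, one case report field and one repeated summary. A few potential controls would be lost. They can be replaced, because Arm 2 has no maximum.
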